6.3 ANALYSIS OF GLUCOSE MEASURES

Mean glucose, glucose measurement indicator (GMI), standard deviation (SD) of glucose and coefficient of variation (CV) of glucose will be evaluated per subject based on CGM output. The GMI and CV are calculated as follows:

$$GMI (\%) = 3.31 + 0.02392 \times (\text{mean glucose in mg/dL})$$

$$CV(\%) = \frac{SD \text{ of glucose}}{\text{mean glucose}}$$

6.4 ANALYSIS OF INSULIN REQUIREMENTS

Insulin requirements (TDI, total daily basal insulin and total daily bolus insulin) during the hybrid closed-loop phase will be compared to the standard therapy phase. The insulin requirements will be collected at Visit 2 (start of ST phase) and compared to the data collected by the Horizon™ System during HCL:

Statistical Analysis Plan

- Total daily insulin: sum of basal and bolus insulin reported over the course of HCL, adjusted for 24-hour period
- Total daily basal insulin: sum of basal insulin reported over the course of HCL, adjusted for 24-hour period
- Total daily bolus insulin: sum of bolus insulin reported over the course of HCL, adjusted for 24-hour period. This will include only bolus insulin administered and recorded by the Horizon™ System.

Data will be summarized both in insulin units and units/kg to provide a weight-adjusted comparison.

6.5 ANALYSIS OF SECONDARY EFFECTIVENESS ENDPOINTS WITH PRESPECIFIED HYPOTHESES

There are two secondary effectiveness endpoints with prespecified hypotheses. The modified Intention to Treat (mITT) analysis set will be the primary analysis set used to analyze the secondary effectiveness endpoints. The results based on the Per Protocol (PP) analysis set will be considered supportive.

Percentage of Time in Range >180 mg/dL

The percentage of TIR >180 mg/dL during Phase 2 of hybrid closed-loop phase will be compared to standard therapy (Phase 1) by calculating the change between the time in range percentages between Phase 2 and Phase 1 for each subject. The change is calculated as the percentage of time in range during Phase 2 minus the percentage of time in range during Phase 1. The null hypothesis associated with this endpoint states that the mean change in percentage of time in range >180 mg/dL is greater than or equal to zero. Rejection of the null hypothesis indicates that the observed data support the alternative hypothesis that the mean change in percentage of time in range >180 mg/dL is less than zero. The hypotheses associated with the second primary effectiveness endpoint are defined as:

$$\begin{aligned} H_0: \mu &\geq 0 \\ H_1: \mu &< 0 \end{aligned}$$

where μ is the mean of the per subject differences in percentage of time in range >180 mg/dL during Phase 2 of hybrid closed-loop compared to the standard therapy phase (Phase 1).

Percentage of Time in Range <70 mg/dL

The percentage of TIR <70 mg/dL during Phase 2 of hybrid closed-loop phase will be compared to standard therapy (Phase 1) by calculating the change between the time in range percentages between Phase 2 and Phase 1 for each subject. The change is

Statistical Analysis Plan

calculated as the percentage of time in range during Phase 2 minus the percentage of time in range during Phase 1. The null hypothesis associated with this endpoint states that the mean change in percentage of time in range <70 mg/dL is greater than or equal to zero. Rejection of the null hypothesis indicates that the observed data support the alternative hypothesis that the mean change in percentage of time in range <70 mg/dL is less than zero. The hypotheses associated with the second primary effectiveness endpoint are defined as:

$$H_0: \mu \geq 0$$

$$H_1: \mu < 0$$

where μ is the mean of the per subject differences in percentage of time in range <70 mg/dL during Phase 2 of hybrid closed-loop compared to the standard therapy phase (Phase 1).

If at least one of the primary effectiveness endpoints are found to be significant, the testing for secondary endpoints can commence. To maintain the family-wise error rate at one-sided 2.5% the testing will commence hierarchically, and Holm's correction will be applied as follows:

- A paired t-test will be applied to each of the secondary endpoints and the unadjusted p-values will be ordered from the smallest to largest.
- The hypothesis associated with the smallest unadjusted p-value will be tested for significance at a one-sided significance level of $2.5\% / 2 = 1.25\%$.
- If the null hypothesis is rejected for the first hypothesis, the testing of the second hypothesis (with the higher unadjusted p-value) will commence, and the hypothesis will be tested for significance at a one-sided significance level of 2.5%. If the first null hypothesis is not rejected, the testing will stop.

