## 13.5 Analysis of Primary and Secondary Endpoints

Both Phase 2 primary effectiveness endpoints will be tested independently of each other for statistical significance using a paired t-test at a one-sided significance level of 1.25%.

If at least one of the Phase 2 primary effectiveness endpoints are found to be significant, the testing for Phase 2 secondary endpoints can commence. The details on how the family-wise error rate will be maintained at the 2.5% significance level (one-sided) will be provided in the Statistical Analysis Plan (SAP). In addition, the Phase 2 primary effectiveness endpoints may also be tested for significance within a smaller cohort of subjects (such as based on age). The details of subgroup analyses and testing will also be detailed in the SAP. At a minimum, the Phase 2 primary effectiveness endpoints will be presented by existing Dexcom G6 use at the time of screening (users and non-users) and by participation in the pre pivotal study (those who participated in the pre pivotal study and those who did not).

There are no hypotheses associated with the other Phase 2 secondary endpoints or any of the Phase 3 endpoints. Summary statistics will be presented by age cohort for all endpoints, stratified by time points of interest (e.g., day vs. night, overall). The Phase 2 primary and secondary endpoints will be summarized for modified Intention to Treat (mITT) and Per Protocol (PP) analysis sets. If the PP analysis set does not differ from the mITT analysis set, separate analyses will not be presented. The data may be stratified by phase of the study, where the data collected in the standard therapy phase of the study will be compared to the data collected in the hybrid closed-loop phase of the study.

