4.1 SAMPLE SIZE

This is a single-arm, multi-center, prospective study. The sample size and study duration were determined to allow for an adequate safety profile of the investigational device. The study will be claimed successful if the incidence rates of severe hypoglycemia and diabetic ketoacidosis are considered acceptable compared to published rates.

In addition, a statistically powered sample size was determined for the two primary effectiveness endpoints. Since each of the primary effectiveness endpoints will be evaluated separately, the significance level will be adjusted so that the overall type I error can be maintained at one-sided 2.5%, and each endpoint will be tested at one-sided 1.25%.

A1C

The sample size estimation is based on the following assumptions:

- Mean difference between paired observations of A1C after at least 6 weeks of continuous Phase 2 participation compared to baseline is -0.5%
- Standard deviation of the difference between paired observations of A1C after at least 6 weeks of continuous Phase 2 participation compared to baseline is 0.8%
- Power of 90% and one-sided significance level of 1.25%

The estimates for the mean difference and standard deviation of the difference between the paired observations were obtained from previous Omnipod studies, where subjects experienced a mean change in A1C of 0.38% over 3 months (standard pump therapy only), from 8.1 to 7.7%, n=85 (data on file). Based on the above assumptions, 35 subjects are required to provide evaluable data.

Statistical Analysis Plan

Percentage of Time in Range 70-180 mg/dL

The sample size estimation is based on the following assumptions:

- Mean difference between paired observations of percentage of time in range 70-180 mg/dL during Phase 2 of hybrid closed-loop compared to the Phase 1 is 10%
- Standard deviation of the difference between paired observations of percentage of time in range 70-180 mg/dL during Phase 2 of hybrid closed-loop compared to Phase 1 is 15%
- Power of 90% and one-sided significance level of 1.25%

The estimates for the mean difference and standard deviation of the difference between the paired observations were obtained from recent Omnipod Horizon feasibility studies, G170012 and G170143, where subjects experienced a mean change in percentage of time in range 70-180 mg/dL of $10.0 \pm 15.1\%$ and $13.8 \pm 14.6\%$, respectively. Based on the above assumptions, 31 subjects are required to provide evaluable data.

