$$\begin{aligned} H_0: \mu &\leq 0 \\ H_1: \mu &> 0 \end{aligned}$$

where μ is the mean of the per subject differences in percentage of time in range 70-180 mg/dL during Phase 2 hybrid closed-loop compared to the standard therapy phase (Phase 1).

Both primary effectiveness endpoints will be tested independently of each other for statistical significance using a paired t-test at a one-sided significance level of 1.25%.

The modified Intention to Treat (mITT) analysis set will be the primary analysis set used to analyze the primary effectiveness endpoints. The results based on the Per Protocol (PP) analysis set will be considered supportive.

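### Testing the secondary endpoints at the full 2.5% after only one of two 1.25% primaries succeeds lets the family-wise error reach about 3.7%, not the stated 2.5%

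*SAP*

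**What the plan says.** SAP section 4.1 sets the split for the two primaries: "overall type I error can be maintained at one-sided 2.5%, and each endpoint will be tested at one-sided 1.25" per cent. Section 4.2 confirms how it is used: "Both primary effectiveness endpoints will be tested independently of each other for statistical significance using a paired t-test at a one-sided significance level of 1.25" per cent.

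Section 6.5 covers time >180 and time <70 mg/dL: "There are two secondary effectiveness endpoints with prespecified hypotheses". The gate is: "If at least one of the primary effectiveness endpoints are found to be significant, the testing for secondary endpoints can commence". The purpose is given next: "To maintain the family-wise error rate at one-sided 2.5% the testing will commence hierarchically", with Holm's correction. For the first step, "The hypothesis associated with the smallest unadjusted p-value will be tested for significance at a one-sided significance level of" 2.5%/2 = 1.25%; the second step, if reached, is at 2.5%. These levels are fixed. Nothing in the SAP lowers them when one primary has failed.

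Protocol section 13.5 has the same gate, commits to a one-sided family-wise rate of 2.5%, and leaves the method to the SAP. Both documents say the SAP prevails where they differ.

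**The concern.** With a Bonferroni split, each primary owns 1.25%. A rejected primary can hand its 1.25% to the next family. A primary that is not rejected cannot, because its 1.25% remains exposed to a false rejection. The SAP nevertheless hands on 2.5% after a single success. The total at risk is then 1.25% on the null primary plus 2.5% on the secondaries.

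What is at stake is a prespecified error-control statement made in both documents. It covers the two secondaries that the sponsor chose to test formally, including time <70 mg/dL, the hypoglycaemia endpoint. A split result, such as a gain in time in range without a gain in A1C, is the case that the at-least-one gate was written for, and it is the case in which control fails.

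**Working it through.** **Inputs**
- From SAP 4.1, 4.2 and 6.5: 1.25% per primary; gate opens on one or two successes; Holm at 1.25% then 2.5%.
- From SAP 4.1: A1C change -0.5 (SD 0.8); time-in-range change 10 (SD 15); 90% power.
- Assumed, because the documents give none: correlations between endpoints, and the SDs of the changes in time >180 and time <70. Ranges are shown.

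**1. The plan's own figures.** A one-sided paired t-test at 1.25% with 90% power needs 35 subjects for A1C (power 90.6%) and 31 for time in range (90.5%). Both match the SAP, so 1.25% is the level in use. The split adds up: 1.25% + 1.25% = 2.5%.

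**2. All four nulls true.** A false secondary rejection can only follow a false primary rejection, so it adds nothing. With independent primaries the rate is 1 - 0.9875² = 2.48%. The stated 2.5% holds.

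**3. Both primary effects real.** The only possible errors are in the secondaries, where Holm holds 2.5%. The stated rate holds again.

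**4. One primary effect real, the other null.** The real effect opens the gate almost always.
- One secondary null, the other real: Holm passes the real one first and tests the null one at 2.5%. Independent statistics give 1 - (1 - 0.0125)(1 - 0.025) = 1 - 0.9875 × 0.975 = **3.72%**.
- Both secondaries null, independent statistics: 1 - 0.9875³ = 3.70%.
- Upper bound under any correlation: 1.25% + 2.5% = **3.75%**.

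**5. Simulation of the full gate and Holm procedure** (2,000,000 draws per row; Monte Carlo standard error about 0.013 percentage points). Correlations are between the A1C and <70 statistics, both scored so that positive means benefit. The last column passes on only the alpha of the rejected primaries.

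| True state | Assumption | SAP rule | Earned alpha only |
|---|---|---|---|
| All null | independent | 2.48% | 2.48% |
| A1C real, other three null | independent | 3.70% | 2.48% |
| TIR and >180 real; A1C and <70 null | correlation 0 | 3.74% | 2.49% |
| same | -0.5 | 3.74% | 2.50% |
| same | +0.3 | 3.61% | 2.42% |
| same | +0.5 | 3.46% | 2.32% |
| same | +0.8 | 3.04% | 2.01% |
| A1C real; TIR, >180, <70 null | three ranges sum to 100%; various SDs | 2.69% to 3.57% | 1.86% to 2.40% |

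The three glucose ranges partition the readings, so the change in TIR equals minus the sum of the changes in >180 and <70. The rows with TIR and >180 real and <70 null have mean effects consistent with this. A separate simulation that imposed the identity on the data (n = 200, 1,000,000 runs, assumed SDs 0.8, 15 and 3) gave 3.72% with independence and 3.75% with assumed correlations. The second row, with independent CGM statistics, ignores the identity; the last row is its realistic counterpart.

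**6. How likely a split result is.** At n = 200 the planning assumptions give standardised effects of 0.5/(0.8/√200) = 8.84 for A1C and 10/(15/√200) = 9.43 for TIR, so each primary has power above 99.99%.

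**The case against.** Four points can be made for the plan.

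- **The family may be only the two secondaries.** Holm does hold 2.5% within that pair, and SAP 4.1 accounts for the primaries separately. This reading does not fit the text well. Both documents attach the family-wise statement directly to the primary gate, and the SAP calls the testing hierarchical. If the narrower meaning was intended, the text would still need to say so.
- **Little depends on it.** Study success is judged on severe hypoglycaemia and DKA rates (SAP 2.5), and SAP 4.2 excludes labeling claims from the primaries. This stands as a limit on consequence. It does not reach the two tested secondaries: the no-claims sentence in SAP 6.6 sits in the section on secondaries without hypotheses, and 6.5 has none.
- **Both primaries will almost surely succeed,** and then the SAP rule and the corrected rule are identical. This stands under the planning assumptions. Those could fail for A1C, which is analysed only in subjects with at least 6 weeks of continuous participation in a study interrupted by a pause.
- **The 3.7% needs a true A1C effect at or very near zero.** If A1C truly improves, rejecting its null is no error and the rate in that scenario is 2.5%. If it truly worsens, the excess fades. With SE = 0.8/√200 = 0.0566 and independence, a true change of +0.01 gives 3.26%, +0.02 gives 2.96% and +0.05 gives 2.59%. This is correct, and it makes 3.7% an extreme, not a typical rate. Family-wise control in the strong sense is a statement about the worst case, so the stated property still fails.

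**Conclusion.** The concern holds. As written, the procedure does not maintain a one-sided family-wise error of 2.5% over the primary and secondary effectiveness tests. With one real and one null primary the bound is 3.75%. The rate is 3.72% with independent statistics when time in range and time >180 improve but A1C and time <70 do not, about 1.5 times the stated rate. Positive correlation lowers it (3.04% at an assumed +0.8), but every case simulated with one real and one null primary exceeded 2.5%. The bound rests only on the levels written in the SAP; the intermediate figures depend on assumed correlations and SDs. Study success is unaffected, and a split result is improbable under the planning assumptions. The error-control statement is nevertheless wrong and should be corrected before any Phase 2 hypothesis is tested.

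**What to change.** In SAP 6.5, set the alpha of the secondary family to the sum of the alphas of the rejected primaries:

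- both primaries significant: Holm at 2.5% (1.25%, then 2.5%), as now;
- exactly one significant: Holm at 1.25% (0.625%, then 1.25%);
- neither significant: no secondary test.

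With one null primary the bound becomes 1.25% + 1.25% = 2.5%. Across the scenarios run, simulated rates did not exceed 2.52%, which is within Monte Carlo error of that bound.

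The edit is one added rule, plus matching changes to the Holm bullets, where 1.25% and 2.5% are now fixed. Protocol 13.5 can stay as it is, since it defers the detail to the SAP. The cost is a stricter secondary level only when one primary fails.

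Two alternatives would also make the text true. One is to require both primaries before the gate opens; this gives about 1.25% in the same one-null-primary cases but loses all secondary testing after a split result. The other is to state that 2.5% applies within the secondary pair only, which gives up the overall control that the protocol promises. Passing on the earned alpha is preferable because it keeps both the gate and the promise.

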6.6 ANALYSIS OF SECONDARY EFFECTIVENESS ENDPOINTS WITHOUT PRESPECIFIED HYPOTHESES

There are no pre-specified hypotheses associated with the other secondary effectiveness endpoints. The mITT analysis set will be the primary analysis set used to analyze the secondary effectiveness endpoints. The results based on the PP analysis set will be considered supportive. Summary statistics will be presented by age cohort for all endpoints, stratified by time points of interest (e.g., day, night, overall). All statistical comparisons will be conducted at a two-sided significance level of 5%, with no adjustment for multiple testing. If the assumptions for parametric tests are grossly violated, a non-parametric method such as Wilcoxon signed rank test may be used. Since the results of endpoint analyses will not be used to support clinical claims, no adjustment for multiplicity will be performed.

Statistical Analysis Plan

As described in this document, results will be stratified by phase of the study (ST and HCL), age group (subjects aged 6-13.9 years and subjects aged 14-70 years) and time of day (daytime: 6AM to <12AM and nighttime: 12AM to <6AM). Results for other subgroups (e.g., demographics, previous pump or CGM use, length of time in HCL) may be presented as appropriate. Data at Visit 13 will be used for any parameters that are measured at end of Phase 2. Data at Visit 19 will be used for any parameters that are measured at end of Phase 3.

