1 PURPOSE

The purpose of this Statistical Analysis Plan (SAP) is to describe the statistical methodology that will be used to confirm the safety and effectiveness of the Omnipod Horizon™ Automated Glucose Control System in patients with type 1 diabetes. Should there be any discrepancy between the pivotal study protocol and this SAP, the content of the SAP shall prevail.

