2.3 STUDY SCHEDULE

The study will consist of a 14-day outpatient standard therapy (ST) outpatient phase (Phase 1), a 13-week outpatient hybrid closed-loop (HCL) phase (Phase 2), and a 6-month hybrid closed-loop extension phase (Phase 3). The sponsor intends to submit results from Phase 2 for marketing clearance after data collection for Phase 2 is complete.

A subset of subjects will participate in supervised challenges during any consecutive 5-day period during the 13-week HCL Phase 2:

- A minimum of 100 subjects 6-13.9 years

Statistical Analysis Plan

- A minimum of 60 subjects 14-70 years

Subjects having completed the prepivotal study may participate in this pivotal study and begin at Visit 5 during Phase 2 (HCL phase) since Phase 1 (ST) was completed as part of the prepivotal study and is not required to be repeated. Prepivotal subjects do not require rescreening if their original screening is within 45-days prior to Visit 5.

The Horizon™ System has two modes. In Manual Mode, the system will function equivalently to the Omnipod DASH System. This includes delivering insulin at programmed basal rates and bolus amounts with the option to set temporary basal profiles. In Automated Mode, the system will support the use of multiple target glucose values. The programmed basal rates, glucose targets and bolus calculator settings will inform the MPC (model predictive control) algorithm for insulin dosing parameters.

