3.3 SECONDARY OBJECTIVE AND ENDPOINTS

The secondary objective is to evaluate additional glycemic measures of effectiveness of the Omnipod Horizon™ Automated Glucose Control System. The secondary objective will be evaluated based on the following per subject endpoints *with* prespecified hypotheses:

- Glucose metrics from system CGM during the hybrid closed-loop phase for Phase 2 will be compared to Phase 1 overall:
 - Percentage of time in range > 180 mg/dL
 - Percentage of time in range < 70 mg/dL

Additional per subject endpoints *without* prespecified hypotheses used to evaluate the secondary objective include:

- A1C:
 - A1C after at least 8 weeks of continuous Phase 2 participation at the end of Phase 2 (Visit 13), 6 months (Visit 16) and the end of Phase 3 (Visit 19)
 - Change from baseline in A1C after at least 6 weeks of continuous Phase 2 participation, after at least 8 weeks of continuous Phase 2 participation, at the end of Phase 2 (Visit 13), 6 months (Visit 16) and the end of Phase 3 (Visit 19)
 - Proportion of subjects demonstrating an improvement from baseline in A1C after at least 6 weeks of continuous Phase 2 participation, after at least 8 weeks of continuous Phase 2 participation, at the end of Phase 2 (Visit 13), 6 months (Visit 16) and the end of Phase 3 (Visit 19)
- Glucose metrics from system CGM during the hybrid closed-loop phase for Phase 2 and Phase 3 will be compared to Phase 1 during the day, overnight, and overall:
 - Mean glucose
 - Percentage of time in range 70-180 mg/dL
 - Percentage of time in range 70-140 mg/dL
 - Percentage of time in range > 180 mg/dL
 - Percentage of time in range ≥ 250 mg/dL
 - Percentage of time in range ≥ 300 mg/dL
 - Percentage of time in range < 70 mg/dL
 - Percentage of time in range < 54 mg/dL
 - Standard deviation
 - Coefficient of variation
- Percentage of time in hybrid closed-loop as proportion of overall device usage time during Phase 2 and Phase 3
- Glucose management indicator (GMI) based on overall mean glucose during Phase 2 and Phase 3 will be compared to Phase 1
- Insulin requirements during Phase 2 and Phase 3 will be compared to Phase 1:

Statistical Analysis Plan

- Total daily insulin (TDI) (units, units/kg)
- Total daily basal insulin (units, units/kg)
- Total daily bolus insulin (units, units/kg)
- Change from baseline in BMI (kg/m^2) at end of Phase 2 and Phase 3

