7 GENERAL STATISTICAL CONSIDERATIONS

7.1 ANALYSIS SETS

The following analysis sets are planned for the study and will apply to the endpoints through the end of Phase 2. There are no prespecified analysis sets for Phase 3; all available data will be used to summarize Phase 3 endpoints.

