7.6 EXPLORATORY ANALYSES

The following exploratory analyses will be considered. The analyses may be used for internal research purposes and/or scientific presentations and/or manuscripts and may not all be provided in a regulatory submission:

- Number of hypoglycemic and hyperglycemic events as measured by the system CGM during the hybrid closed-loop phase will be compared to the standard therapy phase
- Glucose metrics from the system CGM during the hybrid closed-loop phase stratified by device mode
- Change from baseline in A1C and BMI at the last follow-up visit, given at least 6 weeks of participation during Phase 2
- Change from baseline in A1C after at least 6 weeks of continuous Phase 2 participation, stratified by baseline A1C (e.g. A1C $\geq 7.5\%$, $\geq 9.0\%$)
- Proportion of subjects with A1C $<7.0\%$ at baseline and after at least 6 weeks of continuous Phase 2 participation; similar analyses using A1C cutoffs of $<7.5\%$, $<8.0\%$ and $<9.0\%$
- Proportion of subjects with change from baseline in A1C after at least 6 weeks of continuous Phase 2 participation of $>0.5\%$ and $>1.0\%$
- Proportion of subjects who either had an improvement from baseline of $>1.0\%$ in A1C or A1C $<7.0\%$ after at least 6 weeks of continuous Phase 2 participation
- Percentage of time the CGM was used during the HCL phase
- Number of meal and correction boluses
- Compare glycemic outcomes (e.g., TIR <70 mg/dL, TIR >180 mg/dL) by bolus frequency per day
- Compare glycemic outcomes (e.g., TIR <70 mg/dL, TIR >180 mg/dL) by use of CGM informed bolus calculator (i.e., days with CGM informed bolus calculator used at least once and days without CGM informed bolus calculator use)
- Post-prandial glucose response including time to peak glucose, peak glucose concentration, peak glucose excursion, to meals with bolus (challenge days 1 and 3) vs no bolus (challenge days 2 and 4)
- Glycemic outcomes and other measures based on evaluable subjects (i.e., those subjects with at least 8 weeks of data during the HCL phase)

Statistical Analysis Plan

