The results of exploratory analyses will be presented using summary statistics. Data at Visit 13 will be used for any parameters that are measured at end of Phase 2 (data at Visit 19 will be used for any parameters that are measured at end of Phase 3). Any statistical testing will be performed at a two-sided significance level of 5% with no adjustment for multiple testing. If the observed data are found not to follow a normal distribution, non-parametric methods may be employed (such as Wilcoxon rank sum test as appropriate).

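### The SAP ends Phase 3 at Visit 19 (Day 270) while the protocol ends it at Visit 23 (Day 450), so end-of-Phase-3 BMI has no scheduled data and end-of-Phase-3 A1C is a mid-phase value

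*SAP*

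**What the plan says.** **SAP.** Section 2.3 describes a "6-month hybrid closed-loop extension phase (Phase 3"). Sections 3.3 and 6 list three secondary A1C items (value, change from baseline, proportion improved), each with time points that include "6 months (Visit 16) and the end of Phase 3 (Visit 19"). Section 3.3 also lists "Change from baseline in BMI (kg/m^2) at end of Phase 2 and Phase 3", and section 6 repeats it. Section 6.6 then sets a general rule: "Data at Visit 19 will be used for any parameters that are measured at end of Phase 3". Section 7.6 repeats that rule for the exploratory analyses: "data at Visit 19 will be used for any parameters that are measured at end of Phase 3".

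**Protocol.** The Protocol Summary, section 5.2 and section 10 give a 12-month Phase 3. Sections 6.3.1 and 13.2.4 place its end at Visit 23, about 15 months in. Section 10.9 makes Visit 23 (Day 450 ± 5) the end of the study. Section 10.5 puts Visit 19 at Day 270 ± 5, and section 10 makes it the latest point for consenting to the second 6-month interval.

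**Precedence.** SAP section 1 says that where the two documents differ, "the content of the SAP shall prevail". Protocol 13.11 says the same and requires deviations from the final SAP to be described in the study report.

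**The concern.** The governing document ends Phase 3 at a visit that the protocol treats as its midpoint. Two things follow.

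- **BMI.** The end-of-Phase-3 change is to be computed at a visit where neither height nor weight is scheduled. SAP 7.5 plans no imputation, so under the stated rule the endpoint is essentially empty, although the trial will collect the data at Visit 23.
- **A1C.** Visit 19 does have an A1C, so the three items can be computed, but a value from about month 9 would carry the label the protocol attaches to about month 15. The SAP names A1C at Visits 21 and 23 nowhere, although protocol 6.2.1 and 13.2.2.1 list both. The planned secondary analyses would therefore not show whether the effect lasts through the second 6 months.

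An analyst who uses Visit 23 instead departs from the SAP and must report a deviation, having chosen the visit outside the plan.

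**Working it through.** **Inputs, all from the protocol.** Phase 3 starts at Visit 13 (section 10), which is Day 94 ± 3 (Table 2). Later visit days and assessments come from Table 3, checked against sections 10.3, 10.5, 10.7, 10.9 and 10.11.

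| Visit | Study Day | A1C | Height and weight |
|---|---|---|---|
| 16 | 180 ± 5 | yes | no |
| 19 | 270 ± 5 | yes | no |
| 21 | 360 ± 5 | yes | no |
| 23 | 450 ± 5 | yes | yes |
| Early withdrawal | any | yes | yes |

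**The protocol's own timing.** 450 / 30 = 15.0 months (450 / 30.44 = 14.8), which reproduces its figure of about 15 months for Visit 23. From Visit 13, 450 − 94 = 356 days, and 356 / 30.44 = 11.7 months, consistent with a 12-month Phase 3.

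**The SAP's timing.** From Visit 13 to Visit 19, 270 − 94 = 176 days, and 176 / 30.44 = 5.8 months. The SAP's 6 months and its Visit 19 therefore agree with each other; the conflict is with the protocol. Visit 19 falls at 270 / 30.44 = 8.9 months.

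**Size of the discrepancy.**

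- Nominal gap: 450 − 270 = 180 days.
- Smallest gap within the windows: 445 − 275 = 170 days.
- Largest gap within the windows: 455 − 265 = 190 days.
- Share of Phase 3 elapsed at Visit 19: 176 / 356 = 49.4%.

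**Endpoints affected.** SAP 3.3 has four secondary items with an end-of-Phase-3 time point. A1C value, A1C change and proportion improved would each take the Day 270 result. BMI change has no scheduled measurement at the named visit. Early-withdrawal visits do record height and weight, but they are not Visit 19.

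**The case against.** **Other SAP text could bring in Visit 23.** Section 7.1 says "all available data will be used to summarize Phase 3 endpoints", and section 7.6 includes "Change from baseline in A1C and BMI at the last follow-up visit, given at least 6 weeks of participation during Phase 2". Both could admit Visit 23 data. However, the first sits in the definition of analysis sets and does not displace a specific visit rule that is stated twice. The second is exploratory, is only to be considered, and may not be submitted. Neither repairs the secondary endpoints.

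**This may be a version lag rather than a choice.** The SAP is consistent within itself and may not have been updated when Phase 3 was lengthened. That is plausible but cannot be confirmed from the documents. It would explain the conflict without removing it, because the current protocol still defers to the SAP.

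**No data are lost.** This stands. A1C is still drawn at Visits 21 and 23, and height and weight are still taken at Visit 23. The fault lies in which visit the plan selects and labels.

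**The month figures are not elapsed time for everyone.** This also stands. Study Days exclude the Phase 2 pause (protocol 9.11), and prepivotal subjects had 14 earlier days of closed-loop use. The 180-day gap between the scheduled Phase 3 visits does not depend on either.

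**Some subjects will have no Visit 23.** Anyone who declines the second interval stops at about Visit 19. The available-data rule in SAP 7.5 covers them, but the number contributing at each visit should be shown.

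**The impact is small.** Protocol 13.5 attaches no hypothesis to any Phase 3 endpoint, and Phase 3 results are submitted separately. This limits the importance of the point without making the rule workable.

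**Conclusion.** The concern holds. Under the prevailing SAP, one secondary endpoint (BMI change at end of Phase 3) has no scheduled data. Three others (the A1C items) use a value from 180 days before the protocol's end of phase, 49% of the way through it. This rests on the nominal visit schedule, on Study Days as the protocol counts them, and on the SAP taking precedence as both documents state. The Phase 2 hypothesis tests, their alpha and power, and the study success criterion in SAP 2.5 are unaffected. It should be corrected before Phase 3 is analysed, but it does not threaten the trial's main conclusions.

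**What to change.** **SAP.**

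- Section 2.3: change Phase 3 to 12 months.
- Sections 3.3, 6, 6.6 and 7.6: define end of Phase 3 as Visit 23. The rule in 6.6 and 7.6 would then name Visit 23 in place of Visit 19.
- Sections 3.3 and 6: keep Visit 19 as an interim A1C time point and add A1C and its change from baseline at Visits 21 and 23, all descriptive, with the number of subjects at each visit.
- Section 3.2: leave unchanged, so that the two Phase 2 endpoints are still tested at one-sided 1.25%.

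If the sponsor means this SAP to cover only the first 6-month interval, it should say so, relabel Visit 19 accordingly and remove the end-of-Phase-3 BMI rule at that visit. A plan for the second interval would then be needed.

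**Protocol.** Sections 6.2.1 and 13.2.2.1 announce two primary effectiveness endpoints and list three bullets. Phase 3 A1C and Phase 3 time in range appear among them, but SAP 3.2 has neither. The Phase 3 A1C analysis text in 13.2.2.1 covers Visit 16 only, and the secondary A1C lists in 6.3.1 and 13.2.4 omit Visits 19 and 21. A short clarification should state where the Phase 3 endpoints belong and which visits they use.

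**Two separate omissions worth aligning in the same amendment.** Neither is caused by the Visit 19 rule.

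- SAP 3.1 does not repeat the Phase 3 severe hypoglycemia and DKA rates per person-month planned in protocol 6.1.1. SAP 5.4 does tabulate adverse events by phase, so only the rate is missing.
- The glucose-metric bullet in SAP 6 drops Phase 3, which SAP 3.3 includes.

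**Cost.** Amendment wording only. No visit or measurement is added, and Phase 2 analysis and submission timing are unaffected.
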